**STUDY SUMMARY**

Name of Sponsor: Relez Therapeutics, LLC	Compound: FDA approved antigens in proprietary preparation	
Title of Protocol: “A double-blind, prospective, parallel group evaluation of a novel novel biologic therapy for perennial allergic rhinitis”	IND No.: Not Applicable	EudraCT No.: Not Applicable
Study Number: PMA 001	Phase: 2 Proof of Concept	

## **1.2 Abstract and Study Design:**

This is a randomized, parallel-group, double-blind, phase 2, single center, proof-of-concept study which will evaluate the effect of a proprietary mixed preparation of FDA approved allergens (PMA) used as a sub-cutaneously administered immunotherapy for the management of allergic rhinitis (perennial and seasonal). Participating study subjects will be required to manifest the signs and symptoms of allergic rhinitis and test positive to at least six allergens using a multi aeroallergen screen at the time of study recruitment. All subjects will undergo standard allergen skin prick testing using six Multi-Test® PC skin prick test devices (Lincoln Diagnostics, Decator, IL) or comparable skin testing technique for a total of 48 SPT. Approximately 36 total subjects will be enrolled.

Following a successful screening study visit and two week medication washout period, a 8 week treatment period will be initiated with bi-weekly study visits being undertaken, through to the end of immunotherapy, for assessment of therapeutic response and safety evaluations. Efficacy evaluation will be monitored using validated instruments that assess study subject clinical response, physician global assessment, and medication use. A safety assessment will be undertaken one month following completion of treatment.

At the screening visit (Screening Visit) a potential study subject will be required to fulfill the requirements of the study inclusion and exclusion criteria, will have a clinical evaluation including medical history and physical examination, blood draw and performance of skin testing. The study subject will then abstain from using intranasal steroids and antihistamines for two weeks and then return to the clinic for administration of sub-cutaneous PMA and post-treatment in-clinic safety evaluation. The latter evaluation period will comprise approximately 60 minutes to assess the study subject's response to PMA immunotherapy. Follow up clinic study visits will continue bi-weekly through 8 weeks and at each of these visits the study subject will receive increasing doses of PMA immunotherapy and will be evaluated for safety. Twice weekly clinical evaluation will also be performed. Following the final administration of PMA immunotherapy, a one month follow-up safety and clinical efficacy evaluation will be conducted by telephone or in the clinic. The duration of the study will be approximately 14 weeks.

### **Primary Objectives:**

To evaluate whether there is a difference in the signs and symptoms of moderate to severe allergic rhinitis when treated with a proprietary mixed preparation of FDA approved allergens, administered sub-cutaneously over a 8-week period, versus the response to placebo and standard of care.

### **Secondary Objectives:**

The secondary objectives of this study are to quantify allergy medication use and adverse events. Serum will also be stored to evaluate changes in IgE and IgG subclasses.

Subject Population: Adult male and female subjects aged 18-65 with moderate to severe allergic rhinitis.	
Number of Subjects: Approximately 36 total study subjects will be recruited Subjects will be equally divided between active treatment and placebo administration.	Number of Sites: Single site
Dose Level(s): All subjects will be started on the same dilution of PMA	Route of Administration: PMA – sub-cutaneous Placebo – sub-cutaneous
Duration of Treatment: 8 weeks	Period of Evaluation: 14 weeks
Main Criteria for Inclusion: 

1. In the opinion of the investigator, the subject is capable of understanding and complying with protocol requirements.

2. The subject signs and dates a written, informed consent form and any required privacy authorization prior to the initiation of any study procedures.

3. The subject is a male or a non-pregnant, non-lactating female between the ages of 18 and 65.

4. The subject is actively manifesting symptoms and signs of moderate to severe allergic PAR with or without SAR component defined as score of at least 28 on the RQLQ and 6 on the TNSS scale. Scores will be determined on the first and second visit (after the 14 day medication washout period). Both scores exceeding their threshold on either day will qualify.

5. Skin test strongly positive (wheal at least 5mm diameter and 2mm greater than negative control) to at least 6 of 48 allergy skin prick tests including at least one species of dust mite.

	
1.3 Exclusion Criteria Any subject who meets any of the following criteria will not qualify for entry into the study: 

1. The subject has received any investigational compound within 30 days prior to screening.

2. The subject has received allergen immunotherapy or SLIT in a previous clinical study or as a therapeutic agent within the past two years.

3. The subject has a history or clinical manifestations of significant medical conditions (cardiovascular, hepatic, infectious or renal disease, etc.) which in the opinion of the

	

investigator renders them unacceptable study subjects.

4. The subject has a history of drug abuse (defined as any chronic illicit drug use) or a history of alcohol abuse within 5 years prior to the screening visit.
5. The subject is required to take excluded medications listed in Section 6.3.
6. If female, the subject is pregnant or lactating or intending to become pregnant before, during, or within 1 month after participating in this study; or intending to donate ova during such time period.
7. Subjects found to have on physical exam significant nasal polyps, septal deviation or infectious sinusitis.
8. The subject has a history of allergic rhinitis but is not currently manifesting active signs and symptoms of the disorder.
9. Subject has a history of cancer, other than squamous cell or basal cell carcinoma of the skin that has not been in full remission for at least 5 years prior to Screening. (A history of treated CIN I, II, or CIN III [cervical intraepithelial neoplasia] is allowed.)

### **Main Criteria for Evaluation and Analyses:**

#### **Primary efficacy endpoint**

The primary efficacy endpoint for this study is the quantitative comparison of the study subject clinical response of active PMA immunotherapy compared to the placebo treatment. The total combined symptom and medication score (DCS) will be used as a validated assessment.

#### **Secondary efficacy endpoints**

The secondary efficacy endpoints for this study are mini-Rhinitis Quality of Life Questionnaire (RQLQ) and safety assessment. Serum will also be stored to evaluate changes in IgE and IgG subclasses.

#### **Safety Analysis**

Safety outcomes will be assessed by adverse event reporting in active and placebo treated study subjects.

Overall safety and tolerability will be assessed by evaluating the incidence of treatment emergent adverse events (TEAE), vital signs, and other safety variables. Treatment-emergent AEs will be defined as any AEs, regardless of relationship to study drug, which occurs on or after the first double blind dose date and up to 30 days after the last dose date of the double-blind study drug.

Treatment-emergent adverse events (treatment at time of event) will be summarized using the Medical Dictionary for Regulatory Agencies (MedDRA) coding dictionary.

### **Statistical Considerations:**

### **Efficacy Analyses**

The intent-to-treat approach will be used. Baseline characteristics (those collected prior to randomization) will be described using mean and standard deviation for continuous variables and medians and ranges for discrete variables.

The primary efficacy variable is the change in symptoms at the end of the periods of PMA or placebo study drug administration. The p-value, least square (LS) treatment means, difference between the LS treatment means, and 95% confidence intervals for the treatment differences will be presented.

The secondary efficacy variables are rescue medication requirement and adverse events. These changes will be analyzed similarly to that of the primary efficacy variable.

The percentage of subjects stopping PMA or placebo administration due to intolerance or lack of efficacy will be summarized by treatment group, and the groups will be compared using Fisher's exact test.

### **Sample Size Justification:**

The study sample size is based upon the results of prior immunotherapy investigations undertaken by the Investigators of this study and their colleagues in the Division of Allergy & Clinical Immunology, Johns Hopkins University School of Medicine. Efficacy for immunotherapy was estimated to be 80% for treatment group and 30% for placebo. Using an error rate ( $\alpha$ ) of 0.05 and 80% Power we calculate a total sample size needed of 28 subjects. To account for drop off we will recruit up to 36 subjects.

## **2.0 STUDY REFERENCE INFORMATION**

### **2.1 Endpoints**

#### **2.1.1 Primary Endpoints**

The primary endpoint is to quantify and compare the clinical difference in signs and symptoms and medication usage that may be apparent when subjects with active perennial allergic rhinitis (PAR) with or without seasonal symptoms (SAR) are treated in a double-blind, prospective, controlled eight weeks study with a PMA versus placebo.

#### **2.1.2 Secondary Endpoint**

The secondary endpoints include the global RQLQ index and adverse events profile (AE). Serum will also be stored for measurement of immunoglobulins at a later date.

### **2.2 Primary Investigator**

The sponsor has selected a Signatory Primary Investigator from the investigators who participate in this study. Selection criteria for this investigator included significant knowledge of the study protocol, the study medication, their expertise in the therapeutic area and the conduct of clinical research as well as study participation. The Signatory Coordinating Investigator will be required to review and sign the clinical study report and by doing so agrees that it accurately describes the results of the study.

## **2.3 List of Abbreviations**

AE	adverse event
AR	allergic rhinitis
BMI	body mass index
CRF	case report form
CRO	contract research organization
CSR	clinical study report
CysLTs	cysteinyl leukotrienes
DCS	Daily combined score
DNA	deoxyribonucleic acid
FDA	Food and Drug Administration
GCP	Good Clinical Practice
HIV	human immunodeficiency virus
ICH	International Conference on Harmonisation
ICS	Inhaled corticosteroids
IgE	Immunoglobulin E
IL	interleukin
INR	international normalized ratio
IRB	institutional review board
LFT	liver function tests
LTRA	leukotriene receptor antagonists
MedDRA	Medical Dictionary for Regulatory Activities
PMA	proprietary mixture of allergens
PAR	perennial allergic rhinitis
PNU	Protein Nitrogen Units
PTE	pretreatment event
RBC	red blood cell
RNA	ribonucleic acid
SAE	serious adverse event
SAP	statistical analysis plan
SAR	seasonal allergic rhinitis

SOP	standard operating procedure
TEAE	treatment emergent adverse event
TNSS	Total nasal symptom score
ULN	upper limit of normal
WHO	World Health Organization

---

### **3.0 INTRODUCTION**

#### **3.1 Background**

##### **Allergic rhinitis and asthma**

Allergic rhinitis (AR) is one of the most common chronic disorders, with reported prevalence ranging from 3% to 19% (1). It is a heterogeneous disorder that includes seasonal AR (SAR) symptoms ('hay fever') and, perennial AR (PAR). The comprehensive review of Kay and colleagues reports that SAR is found in approximately 10% of the general population and PAR in 10% to 20%. (2).

Clinical symptoms of AR include runny nose, itching, sneezing and nasal congestion. More than 80% of persons with allergic asthma have AR and AR is a risk factor for the development of asthma. Hence, there is a significant comorbidity between asthma and AR which is not surprising since there is an uninterrupted air passage from the nose to the alveolar ducts of the lungs. The clearest connection between AR and asthma is based on a shared immunologic response to an identified foreign substance. The term often used for the response is 'allergy', and the foreign substance is an allergen. Kay (2) notes that when Clemens von Pirquet originally introduced the term allergy in 1906, he had applied it to the reactivity found in both protective immunity and hypersensitivity. However, allergy is now identified with the type 1 hypersensitivity disorder of the immune system associated with immunoglobulin E (IgE).

##### **Triggers for episodes of allergic rhinitis**

The triggers for AR are aeroallergens associated with, airborne pollens, dust mites, animal dander, molds that induce IgE production. The inflammatory response is similar for both AR and asthma; they share a similar respiratory epithelial structure of ciliated pseudostratified columnar epithelium with goblet cells (6). The pathophysiology of local mediator release, systemic immune response and eosinophil recruitment are alike. During the early-phase response, symptoms in patients with AR typically consist of sneezing, rhinorrhea and conjunctivitis; patients with asthma experience wheezing, coughing and shortness of breath, in addition to objectively demonstrable changes in lung function. There is a similar pattern and time course of early- and late-phase responses in AR and asthma. Approximately 1 hour after allergen provocation, patients with AR experience a peak in symptoms, while patients with asthma experience a steep decline in lung function, measured by forced expiratory volume in 1 second (FEV1). During the late-phase response, nasal congestion is sustained in patients with AR, while a prolonged fall in lung function is again observed in patients with asthma. Within 12 h to 24 h, both types of reactions may resolve.

##### **Sub-cutaneous allergen immunotherapy**

Allergen immunotherapy by injection (desensitization or hyposensitisation) consists of an induction course of injections of increasing doses of the allergen extract, usually given weekly or bi-weekly. The maintenance phase of maximum dosage injections usually lasts between three to 5 years (7). Injections can consist of single or mixed allergen extracts. As reported in a recent Cochrane Review, specific allergen immunotherapy (SIT) for hay fever is widely considered to be effective where grass pollen, ragweed, and birch pollen are causal agents, and there is evidence that its efficacy may continue for many years beyond the treatment period (8). The review concludes that specific allergen injection immunotherapy is a safe and efficacious treatment in reducing symptom severity and the requirement for anti-allergic medication in AR. In view of the occasional occurrence of systemic side effects following injections, it is customary that injection immunotherapy is performed in the immediate presence of a physician and administered by personnel that are fully trained and who are experienced in the early recognition and treatment of such reactions.

### **3.2 Rationale for the Proposed Study**

The proposed study represents a novel and heretofore unpublished method of sub-cutaneous immunotherapy for the management of the spectrum of PAR with or without SAR. The immunologic concept and therapeutic management techniques to be studied in this investigation evolved during the past three decades in the clinical practice observations of some 20,000 patients as undertaken by the “inventor” of the treatment paradigm, [name], a Johns Hopkins University School of Medicine graduate and Diplomate of The American Board of Otolaryngology.

The intrinsic difference of the [name] technique, compared to currently used methodologies of sub-cutaneous immunotherapy for AR, is that a wide-spectrum proprietary mixture of 60 different FDA approved allergens (referenced above as PMA), refined over multiple years of clinical testing and observation, is used for the immunotherapy. In part due to the significantly lower dose of each active allergen, this form of immunotherapy has demonstrated an excellent clinical safety profile and not one single anaphylactoid response has been noted with the use of this proprietary mixture in decades of use and development.

Current sub-cutaneous immunotherapy for the management of AR typically consist of the use of a limited number of relevant antigens (grass pollen, tree pollen, ragweed pollen, dust mites, etc.). Hence, the proprietary antigen mixture that will be used in this investigation that uses more than 60 relevant allergens represents a new immunologic concept that has not been subjected to a controlled, parallel group, prospective and double-blind study.

All the antigens used in the PMA are currently FDA approved for immunotherapy purposes. These consist of both standardized and non-standardized forms of allergen. For the standardized allergen extracts, manufacturers compare the allergen extract to a U.S. reference standard for potency, maintained by the FDA Center for Biologics Evaluation and Research. The precise selection of

antigens, the quantitative amount of the latter in the proprietary mixture and the preparation of three allergenic solutions of “vaccine” for immunotherapy are proprietary intellectual property.

## **4.0 STUDY OBJECTIVES AND ENDPOINTS**

### **4.1.1 Primary Objective**

The primary efficacy endpoint for this study is the quantitative comparison of the study subject clinical response of active PMA immunotherapy compared to the placebo treatment. The Total Nasal Symptoms Score (TNSS) will be used to generate daily symptom scores. The total combined daily symptom and medication score (DCS) will be used as the primary validated assessment.

### **4.1.2 Secondary Objective**

The secondary efficacy endpoints for this study are mini-Rhinitis Quality of Life Questionnaire (RQLQ) and safety assessment. Serum will also be stored to evaluate changes in IgE and IgG subclasses.

## **5.0 STUDY DESIGN AND METHODS**

### **5.1 Study Design**

This is a phase 2 proof of concept study. It is being undertaken to characterize and quantify the clinical difference in signs and symptoms that may evolve when subjects with active SAR/PAR are administered a sub-cutaneous form of immunotherapy in a double-blind, prospective, controlled six weeks study wherein a PMA is compared with saline placebo.

Randomization to active PMA versus placebo treatment is on a 1 to 1 ratio. A double-blind study design is used to minimize outcome bias. Randomization measures to minimize bias at study entry include computerized random assignment of treatment versus placebo vials.

Subjects who are receiving nasal steroids for their SAR/PAR at screening may continue in the screening process if they agree to discontinue their therapy and commence a 14 day wash-out period of their medication prior to receiving active/placebo immunotherapy. Potential study subjects who, at screening, are not on active treatment for their SAR/PAR and asthma may enter directly into the investigation provided they fulfil entry and exclusion criteria and screening testing requirements.

The population to be studied consists of male and female adults aged 18 years to 65 years who are actively manifesting SAR/PAR have a score of at least 28 on the mini-RQLQ and 6 on the TNSS scale.

[figure not shown]
The active treatment phase of the study will be for six weeks with a safety followup assessment at 30 days post-treatment. No interim analysis is planned.

The study immunotherapy that will be evaluated in this study is a new innovative proprietary mixture of FDA approved allergens which has been clinically developed and evaluated, during the past three decades, in some 20,000 patients by the inventor of the mixture (see 3.2). In clinical evaluation this patented antigen mixture has provided clinical symptomatic relief to patients with SAR/PAR in as brief a period as three administrations of immunotherapy injections and has an observed overall success rate of approximately 80 to 90 percent of such treated subjects.

In this study approximately 36 study subjects will be equally randomized to active PMA or placebo. The duration of active PMA or placebo treatment will be 8 weeks with clinic visits twice-weekly during this period and a post-treatment safety follow up assessment at one month following the final administration of immunotherapy. All doses of immunotherapy will be administered in the study site clinic by the investigators or their designees.

A schematic of the study design is included as Figure 5.a. A schedule of assessments is listed in Appendix A.

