#### *7.1.4 Immunotherapy Dose and Regimen*

Recruited subjects alternate to be assigned either treatment set I or II (representing either placebo or active PMA treatment in a binded fashion). The assigned treatment set will remain for the duration of the study for each subject. On the day of an injection, 0.3ml from each of the appropriate vial set mix (A-C) will be combined in a sterile 5 ml bottle. Using a new sterile syringe, 0.15-0.60ml of the PMA solution or placebo will be removed for injection purposes according to the injection schedule (Appendix I). A sterile 27G ½ inch syringe will be used for administration. Immunotherapy will be administered bi-weekly in the study clinic for a total of eight consecutive weeks. Appendix I lists the precise immunotherapy injection schedule.

All patients are required to remain in the clinic under close observation by the study nurse for a period of 30 minutes following their injection. A physician is required to be present in the clinic at all times. In addition, one of the investigators must be present on campus and available by cell phone during scheduled treatment sessions. Emergency medications such as albuterol, oxygen, diphenhydramine, and at least two epi-pens will be readily available in the treatment area.

It is important to note that the maximum concentration of each individual allergen is quite low compared to more traditional immunotherapy regimens. The maximum PNU/ml (Protein Nitrogen Units) in vial #1 will be no more than about 180 PNU/ml per allergen (eg 0.9ml of 20,000 PNU/ml stock material into 100ml solution). In most cases the actual concentration of each stock allergen is much lower than 20,000 PNU/ml since the material may be provided as a mixture of several allergens. We would estimate therefore that subjects would receive no more than about 7.2 PNU of antigen contained in the highest injection (0.2ml Vial #2). Typically, allergens are administered via immunotherapy in a range of about 2000 PNU. Thus the dosage of each allergen is less than 0.36% of a typical dose administered in our clinics. The lower overall dosing scheme provided in this study would therefore be considered to be extremely safe with minimal adverse events.

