#### **8.3.2 Study Entrance Randomization**

Study Randomization will take place on study day 1 (Visit 1). The following procedures will be performed and documented during Study Randomization:

- If the subject has satisfied all of the inclusion criteria and none of the exclusion criteria for randomization and the investigator deems the laboratory screening and skin testing are acceptable for continuance in the investigation, the subject should be randomized using the randomization sequence provided by the sponsor.
- Subjects will receive their first sub-cutaneous administration of immunotherapy with dose vial #5.
- The procedure for documenting Screening failures is provided in Section 8.1.11.

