### 8.3.3 Treatment Phase

Study visits 1 through 12 will be conducted (Figure 6a) in the study clinic and at each of these visits the study subject will have a safety and efficacy assessment and if deemed appropriate by the investigator will receive their next sub-cutaneous administration of study immunotherapy. A 60 minute post treatment in-clinic safety assessment will be conducted.

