## **9.2 Procedures**

### **9.2.1 Collection and Reporting of AEs**

#### ***9.2.1.1 PTE and AE Collection Period***

Collection of PTEs will commence from the time the subject signs the informed consent to participate in the study and continue until the subject is first administered study immunotherapy (visit 2) or until screen failure. For subjects who discontinue prior to study immunotherapy administration, PTEs are collected until the subject discontinues study participation.

Collection of AEs will commence from the time that the subject is first administered study immunotherapy (visit 2). Routine collection of AEs will continue until visit 14 .

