## **STUDY OVERVIEW**

### **Endpoints**

#### **Primary Endpoints**

The primary endpoint is to quantify and compare the clinical difference in signs and symptoms and medication usage as well as the global RQLQ index that may be apparent when subjects with active perennial allergic rhinitis (PAR) with or without seasonal symptoms (SAR) are treated in a double-blind, prospective, controlled eight weeks study with a proprietary mixture of FDA approved allergens (PMA) versus placebo.

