## STUDY DESIGN AND METHODS

### Study Design

This is a phase 2 proof of concept study. It is being undertaken to characterize and quantify the clinical difference in signs and symptoms that may evolve when subjects with active seasonal or perennial allergic rhinitis (SAR/PAR) are administered a sub-cutaneous form of immunotherapy in a double-blind, prospective, controlled six weeks study wherein a proprietary mixture of FDA approved allergens (PMA) is compared with saline placebo.

Randomization to active PMA versus placebo treatment is on a 1 to 1 ratio. A double-blind study design is used to minimize outcome bias. Randomization measures to minimize bias at study entry include computerized random assignment of treatment versus placebo vials.

Subjects who are receiving nasal steroids for their SAR/PAR at screening may continue in the screening process if they agree to discontinue their therapy and commence a 14-day wash-out period of their medication prior to receiving active/placebo immunotherapy. Potential study subjects who, at screening, are not on active treatment for their SAR/PAR and asthma may enter directly into the investigation provided they fulfil entry and exclusion criteria and screening testing requirements.

The population to be studied consists of male and female adults aged 18 years to 65 years who are actively manifesting SAR/PAR have a score of at least 28 on the mini-RQLQ and 6 on the TNSS scale.

[figure not shown]
The active treatment phase of the study will be for six weeks with a safety follow-up assessment at 30 days post-treatment. No interim analysis is planned.

The study immunotherapy that will be evaluated in this study is a new innovative proprietary mixture of FDA approved allergens which has been clinically developed and evaluated, during the past three decades, in some 20,000 patients by the inventor of the mixture (see 3.2). In clinical evaluation this patented antigen mixture has provided clinical symptomatic relief to patients with SAR/PAR in as brief a period as three administrations of immunotherapy injections and has an observed overall success rate of approximately 80 to 90 percent of such treated subjects.

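### Protocol 9.2.1.1 ends routine AE collection at visit 14, before the three highest-dose injections, in conflict with Appendix A and the 30-day TEAE window; leftover six-week and visit-number wording also needs correcting

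*Combined protocol and SAP*

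**What the plan says.** **AE period.** Protocol 9.2.1.1 starts AE collection at the first injection, which it places at visit 2, and then states: "Routine collection of AEs will continue until visit 14". Section 9.2.2 ties its SAE procedure to that collection period. Afterwards it asks only for SAEs that are spontaneously reported and considered related to study participation. Section 9.2.1.2 requires AEs to be assessed at each study visit. Appendix A marks AE assessment for visits 2 to 17 and for visit 18 (week 14). Section 12.1.4 defines treatment-emergent events up to 30 days after the last dose.

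**Duration.** Protocol 5.1 calls the trial a six-week study and adds: "The active treatment phase of the study will be for six weeks with a safety followup assessment at 30 days post-treatment". A few lines later it says: "The duration of active PMA or placebo treatment will be 8 weeks with clinic visits twice-weekly during this period". The SAP Study Design section has the same pair of statements ("The active treatment phase of the study will be for six weeks with a safety follow-up assessment at 30 days post-treatment", then eight weeks), while the SAP Primary Endpoints section describes a "controlled eight weeks study with a proprietary mixture of FDA approved allergens (PMA) versus placebo". Section 7.1.4 says: "Immunotherapy will be administered bi-weekly in the study clinic for a total of eight consecutive weeks".

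**Visit numbers.** Section 8.3.1 and Appendix A make visit 1 the screening visit. Section 8.3.2 nevertheless states "Study Randomization will take place on study day 1 (Visit 1") and gives the first injection there. Section 8.3.3 states "Study visits 1 through 12 will be conducted (Figure 6a) in the study clinic". Appendices A and H put the injections at visits 2 to 17.

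**The concern.** The end of AE collection is an operative safety rule, and two parts of the protocol give different answers. The sentence before the visit 14 limit uses visit 2 in the Appendix A and H numbering, so a coordinator would naturally read visit 14 in the same numbering. On that reading, routine collection closes while the dose is still rising, and the data for the last part of the TEAE window in 12.1.4 are not routinely gathered. In an escalating allergen regimen, that is where reactions matter most.

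The six-week wording and the visit numbers in 8.3.2 and 8.3.3 matter less. Alone they would be close to clerical. They belong here because they use the same visit map, and a monitor checking one section against another cannot tell which governs.

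**Working it through.** **1. Which duration is intended?** Twice-weekly visits for eight weeks give 8 × 2 = 16 injections. Appendix H lists 16, at visits 2 to 17, and Appendix A agrees. Six weeks would give 6 × 2 = 12 injections, ending at visit 13 on vial #3. The SAP's primary comparisons use visits 2, 17 and 18. Eight weeks is the plan.

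**2. Does the calendar agree?** Assume screening on day 0 (week 1 = days 0 to 6) and injections 3.5 days apart.

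| First injection | Course | Last injection | Plus 30 days |
|---|---|---|---|
| Day 14 (start of week 3) | 8 weeks | 14 + 15 × 3.5 = day 66.5 (week 10) | day 96.5 (week 14) |
| Day 20 (end of week 3) | 8 weeks | 20 + 15 × 3.5 = day 72.5 (week 11) | day 102.5 (week 15) |
| Day 14 | 6 weeks | 14 + 11 × 3.5 = day 52.5 (week 8) | day 82.5 (week 12) |
| Day 20 | 6 weeks | 20 + 11 × 3.5 = day 58.5 (week 9) | day 88.5 (week 13) |

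A week 14 follow-up visit fits only the eight-week course. The second row also shows that Appendix A's treatment label of weeks 3 to 11 is valid for an eight-week course that starts late in week 3.

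**3. How much dosing follows a literal visit 14?** The inputs are the Appendix H volumes per mix (0.05, 0.10, 0.15 and 0.20 ml for each vial, sum 0.50) and the dilutions. Dose is volume × dilution, in ml of vial #1 equivalent.

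- Nominal dilutions 1/625, 1/125, 1/25 and 1/5: total = 0.50 × (0.0016 + 0.008 + 0.04 + 0.2) = 0.1248. Visits 15 to 17 = (0.10 + 0.15 + 0.20)/5 = 0.0900. Share = 0.0900/0.1248 = 72.1%.
- Preparation volumes in 7.1.1: #2 = 20/105 = 0.1905; #3 = 4/89 = 0.0449; #4 = 0.1905 × 4/89 = 0.00856; #5 = 0.0449 × 4/89 = 0.00202. Total = 0.50 × 0.2460 = 0.1230. Visits 15 to 17 = 0.45 × 0.1905 = 0.0857. Share = 69.7%.
- If collection is taken to stop before visit 14 itself, four injections fall outside: 0.50/5 = 0.1000, or 80% of the nominal total.

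The nominal doses at visits 14 to 17 are 0.010, 0.020, 0.030 and 0.040, so visits 15 to 17 are the three highest of the 16.

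**4. How much of the TEAE window is outside?** With the first injection on day 14 and 3.5-day spacing, visit 14 falls on day 14 + 12 × 3.5 = 56. The window runs from day 14 to day 96.5, which is 82.5 days. Collection to visit 14 covers 42.0 days (51%) and leaves 40.5 days (49%).

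**5. What if visit 14 is a slip?** Section 8.1.9 and Appendix A put the final visit in week 14. A six-week schedule would have screening at visit 1, injections at visits 2 to 13 and follow-up at visit 14. Either origin means that the intended end was the final follow-up visit. The documents do not say which applies. On either, the losses in steps 3 and 4 are zero.

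**The case against.** The strongest reply is that one number in 9.2.1.1 stands against everything else. The sentence limits only routine collection. Section 9.2.1.2 requires AE assessment at each visit and documentation of all AEs, Appendix A carries the assessment through visit 18, 8.3.4 and 8.3.5 require a safety assessment at visit 18, and 12.1.4 fixes the analysis window. Staff working from Appendices A and H would dose correctly and would probably keep asking about AEs. This stands as a limit on the practical risk. It does not settle the conflict, because 9.2.1.1 is the section that defines the period and 9.2.2 refers back to that period.

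Four stronger readings are tempting, and the documents do not support them:

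- *SAE reporting stops at visit 14.* It does not. Section 9.2.2 narrows to spontaneously reported, related SAEs, and Appendix B item 12 requires notification within 24 hours with no end date. What would lapse is the 9.2.2 duty to report every SAE regardless of relatedness.
- *The sponsor plans to stop safety collection early.* The other sections show a drafting conflict, not a settled plan.
- *Subjects might receive only six weeks of treatment.* Section 7.1.4 and Appendices A and H fix 16 injections over eight weeks.
- *Appendix A's weeks 3 to 11 contradict eight weeks.* They do not, as step 2 of the working shows. Shortening the label to weeks 3 to 10 would be wrong for subjects who start late in week 3.

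On 8.3.2, protocol 5.1 lets subjects who are not on active treatment enter directly, so randomization at visit 1 might fit some of them. It cannot fit subjects who need the washout, and 9.2.1.1 and Appendices A and H put the first injection at visit 2 without exception.

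**Conclusion.** The point holds as an internal inconsistency that should be fixed, led by 9.2.1.1. Read literally, routine AE collection ends before three of 16 injections, which carry about 72% of scheduled allergen at nominal dilutions (69.7% by the stated preparation volumes), and before the 30-day follow-up. About half of the TEAE window then lies outside collection, assuming evenly spaced visits. These figures describe the literal reading only. They are not an expected loss of data, and they are zero if visit 14 means week 14. The six-week wording and the visit numbers in 8.3.2 and 8.3.3 are leftovers that leave the intended design clear.

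**What to change.** The essential edit is in 9.2.1.1: run routine AE collection *until visit 18 (week 14, 30 days after the last dose)*. The 9.2.2 SAE procedure and the 12.1.4 window then cover the same period.

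Make these consistency edits in the same amendment:

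- Protocol 5.1 and SAP Study Design: change six weeks to eight weeks, twice in each.
- Section 8.3.3: give the treatment visits as 2 through 17.
- Section 8.3.2: place randomization and the first injection at visit 2.
- Appendix A: leave weeks 3 to 11 as they are.

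The cost is a wording amendment to five sections. It adds no patients, visits or procedures beyond those already in Appendix A, and it leaves dosing, sample size, endpoints and tests unchanged.
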